Level 2 (person) $\pi_{0jk}=\beta_{00k}+r_{0jk}$	coded as 1 if the intervention is implemented in the current (or prior) 3-month period; and otherwise coded as 0. IntvQtr will be the number of quarters since the intervention was applied. We will examine the nature of growth in the outcome as a function of IntvQtr and introduce terms to account for non-linearity as needed. The model to be fit, expressed as a 3-level model fits the "jump" in outcome due to the introduction of the intervention (via the coefficient for γ_{100}) as well as the "slope" over time due to the intervention (via the coefficient for γ_{200}). To examine the impact of removing the intervention, we will further consider a model that introduces two additional time varying covariates (not shown): RemInt coded as 1 if the intervention was removed in the current (or prior) 3-month period, and otherwise coded as 0. This accounts for any deterioration in sleep outcomes when the intervention is ended. RemIntQtr is the number of quarters since the intervention was removed, capturing the change in the slope over time. We will examine the nature of growth in the outcome as a function of RemIntQtr and introduce terms to account for non-linearity as well.
$\pi_{1jk}=\beta_{10k}$	
$\pi_{2jk}=\beta_{20k}$	
Level 3 (unit) $\beta_{00k}=\gamma_{000}+u_{000}$	
$\beta_{10k}=\gamma_{100}$	
$\beta_{20k}=\gamma_{200}$	

Table 5: Final Sample Size (per unit) as Function of Consent % and Attrition % from a 40-Subject Unit

	Consent (%)			
Attrition (%)	45%	50%	55%	60%
25%	13	15	16	18
30%	12	14	15	16
35%	11	13	14	15
40%	10	12	13	14

Table 6: Detectable standardized effect as a function of final sample size per unit and ICC size

ICC	Final Sample size (per unit)				
	10	12	14	16	18
0	0.50	0.45	0.42	0.39	.37
0.10	0.58	0.54	0.51	0.48	.47
0.20	0.65	0.60	0.57	0.55	.53
0.30	0.69	0.65	0.62	0.59	.57
0.40	0.75	0.70	0.66	0.63	.60

the number of participants in the unit, 2) the consent rate, and 3) the attrition rate. Using the expected unit size of 40, Table 5 shows the final sample size as a function of consent and the attrition rates. These final sample sizes (per unit) are used in the following power calculations (which assume six units, 80% power, alpha of .05, and 2-tailed tests).

Power Analysis of Scheduled Study Assessments: For the analysis of the scheduled study assessments, the primary analysis will test the average of the outcome at baseline versus post-treatment and 3-months. The

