We are currently studying a sleep improvement program that combines successful aspects of a multi-component sleep intervention tested in prior work¹² with the structure used in a successful clinician-delivered intervention for antidepressant medication reduction and non-pharmacological depression care in non-dementia SNF units.¹³ This supplemental funding will enable us to 1) revise a sleep intervention approach using a plan-do-study-act^{14,15} approach in one ADRD unit and 2) test that revised approach in a second ADRD unit. We will use the framework of our ongoing trial, with adjustments to content areas (adding strategies specifically for residents with Alzheimer's Disease and sleep problems) and primary outcome measures (less reliance on patient questionnaires and greater reliance on objective and observational outcomes).

The ADRD-specific Improving Sleep Using Mentored Behavioral and Environmental Restructuring (SLUMBER) for Residents with Dementia (SLUMBER-RD) is a non-pharmacological intervention program, delivered by mentoring facility staff who work directly with residents. SLUMBER consists of three core components: **1) improving the nighttime sleep environment; 2) increasing patient activity during the day and reducing daytime behaviors that lead to sleep disturbances at night; and 3) identifying and assisting individual residents experiencing difficulties with sleep.** The specific aims of this supplemental funding request are:

Aim 1: Revise and optimize ADRD-specific SLUMBER-RD components to ensure feasibility on ADRD units.

Hypothesis 1: SLUMBER-RD is feasible as demonstrated by adequate subject recruitment, compliance with wearing wrist actigraphy, and nursing staff participation in providing feedback and implementing behavioral approaches on the selected Alzheimer's disease units.

Aim 2: Test whether SLUMBER-RD improves objectively measured sleep quality in dementia care units.

Hypothesis 2: Residents of units receiving SLUMBER will achieve better nighttime sleep quality quantified by increased total sleep time and reduced number of awakenings measured objectively with wrist actigraphy.

Aim 3: Test whether the SLUMBER intervention improves behavioral symptoms of dementia and engagement in facility activities.

Hypothesis 3: Residents of units receiving the SLUMBER intervention will demonstrate reduced behavioral symptoms of dementia and increased engagement in facility activities.

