2. : Because this is a two-unit supplement to the parent study, we will conduct this intervention in parallel to the ongoing trial, which focuses on units that are not focused on care for residents with ADRD. Although we recognize that some residents on the units within the parent study have dementia, they have less severe behavioral issues than what would warrant being on a unit whose care is more dementia-specific. We aim to conduct the modified SLUMBER-RD intervention in parallel to our other work, thus benefitting from economies of scale in utilizing training times and travel needed to complete work on the parent grant, coordinating technology use with our software company, CaseWorthy™, and research meetings utilizing shared learnings between dementia and non-dementia-specific work. The two units (one in each of two facilities) will be engaged in randomized order (coin-flip). The first unit will provide experience and subsequent modifications for the second unit. Because these two units are in separate facilities, the stagger time for the second unit is only dependent upon completing enough intervention time on the first unit to provide enhanced modifications to the

SLUMBER Protocol V.8/27/2018

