second unit intervention (i.e., some overlap would be feasible). In SLUMBER and SLUMBER-RD, every unit provides baseline and follow-up data. We will collect baseline actigraphy and observational data just prior to the intervention on each unit and within 1 month after a 3-month exposure to the SLUMBER-RD program. Staff will be encouraged to continue to use intervention approaches after the 3-month intervention period and we will leave study resources at the site for ongoing use. We will collect additional follow-up sleep and activity data with repeat wrist actigraph measures, as well as observations at three months after the post-intervention period, similar to what we are doing in the parent R01; however, further follow-up will be truncated due to the one-year time frame for the supplement. **From the intervention beginning and throughout the remaining study duration, real-time environmental data (noise) and observed sleep disturbance will be available to SNF staff on a visible computer interface (described below) to facilitate continued use of SLUMBER strategies.** MDS 3.0 data collection will provide repeated measures of mood and cognitive function for the full study duration. We selected a 3-month follow-up time point to strike a balance between sufficient time for intervention effects to emerge while considering the rapidly changing health status of LTC residents, especially those with ADRD. Moreover, MDS data are collected quarterly and the intervention itself includes an initial mentoring session, two additional meetings over the next two months, and a follow-up session at the end of three months. Because we are interested in a measure of trend for the MDS measures of mood and cognition, we will include two quarters of data for each resident that precedes their time of enrollment.

B. Characteristics of the Research Population

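### SLUMBER-RD Aims 2 and 3 are worded as tests of whether the programme works, but the two-unit before/after design cannot attribute a change to it

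*Combined protocol and SAP*

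**What the plan says.** The section A. Specific Aims (SLUMBER-RD) gives the two dementia (ADRD) units different jobs. The programme is revised in one, and the supplement will then "test that revised approach in a second ADRD unit". The Supplement Design part of A5 confirms the split: "The first unit will provide experience and subsequent modifications for the second unit". The units are in different facilities, both receive the intervention, and a coin flip decides only which goes first.

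Aim 2 is to "Test whether SLUMBER-RD improves objectively measured sleep quality in dementia care units". Aim 3 is to "Test whether the SLUMBER intervention improves behavioral symptoms of dementia and engagement in facility activities". Each carries a directional hypothesis about units receiving the programme.

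On data, the Supplement Design says: "In SLUMBER and SLUMBER-RD, every unit provides baseline and follow-up data". For the outcomes of Aims 2 and 3 it adds: "We will collect baseline actigraphy and observational data just prior to the intervention on each unit and within 1 month after a 3-month exposure". A further follow-up comes three months later. Only the MDS (Minimum Data Set) measures of mood and cognition have a longer run-in, for which "we will include two quarters of data for each resident that precedes their time of enrollment".

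C6 has no SLUMBER-RD analysis, sample size or power statement. The aims section says only that the framework of the ongoing trial will be used.

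**The concern.** The revised programme is observed before and after in one unit. A change in staffing, season, an outbreak or a new facility policy between baseline and follow-up would affect all residents of that unit together and would coincide with the programme. A resident-level test treats residents as independent and would count such a shift as programme effect.

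The protocol gives reasons to take this seriously. A4 reports that facility characteristics and routines, rather than residents' own characteristics and needs, determined day and night bed routines. Threats to Internal Validity in C6 accepts, while calling it unlikely, that residents may improve for reasons unrelated to the programme. It relies on MDS data from before the intervention and on staggered introduction. In the supplement the first safeguard does not reach the outcomes of Aims 2 and 3. The second shrinks to two units that receive different versions.

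The supplement is meant to lead to a large-scale trial in dementia care units. If a before/after p-value were read as evidence of efficacy, that trial could be justified or sized on the wrong basis.

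**Working it through.** **1. The plan's nearest figure.** No detectable effect is stated for SLUMBER-RD. The closest is Table 7 of the parent trial (six units, six steps, alpha .05 two-sided, 80% power). The Hussey-Hughes stepped-wedge variance is

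Var = I·s²(s² + T·t²) / [(I·U − W)s² + (U² + I·T·U − T·W − I·V)t²]

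with I units, T periods, U treated unit-periods, W the sum of squared column totals, V the sum of squared row totals, s² = 1/n and t² = ICC/(1 − ICC), the effect being in within-unit SDs. For I = 6 and T = 7: U = 21, W = V = 91, and the bracketed coefficients are 35 and 140. The detectable effect is 2.80·√Var. At n = 15 this gives .30, .39 and .39 for ICC 0, .20 and .40, as printed. All nine cells of Table 7 reproduce to two decimals.

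**2. The same formula with one unit.** Each period total is 0 or 1, so W = U, and V = U². Both coefficients vanish: I·U − W = U − U = 0, and U² + T·U − T·U − U² = 0. The variance is infinite. Once a period effect is allowed, the programme effect is not identified, however many residents are enrolled.

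**3. Two units, taken generously.** Suppose both were measured on a shared three-period calendar, which is not the planned schedule, and had received the same version. Then U = 3, W = V = 5, and the coefficients are 1 and 2. At n = 15 the detectable effect is 1.02, 1.23 and 1.24 SD for ICC 0, .20 and .40. The parent trial's target is .60.

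**4. Size of the attribution problem (illustration).** Inputs:
- Residents per unit: 12 to 15. This is the 50% consent column of Table 5 for a 40-bed unit with 40% to 25% attrition, carried over from the parent trial as an assumption.
- Within-resident correlation .5: assumed.
- Contrast: baseline against the mean of the two follow-ups, as in the parent analysis of scheduled assessments in C6.
- Drift of the unit's mean, SD d: assumed. The documents give no value, so a range is shown.

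SE = √[(1 − .5)(1 + 1/2)/N], which is .250 SD at N = 12 and .224 SD at N = 15. With no drift, the detectable change is 2.80·SE = .70 and .63 SD.

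False-positive rate of a nominal 5% test = 2Φ(−1.96·SE/√(SE² + d²)):

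| Drift SD | N = 12 | N = 15 |
|---|---|---|
| 0 | 5.0% | 5.0% |
| .05 | 5.5% | 5.6% |
| .1 | 6.9% | 7.4% |
| .2 | 12.6% | 14.4% |
| .3 | 21.0% | 24.1% |

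More residents make it worse, because SE falls while d does not.

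**5. Does pooling help?** With independent drift in two units of equal size, SE² and d² are both halved, so their ratio and every rate in the table are unchanged. A test that uses the unit as the replicate has one degree of freedom and a critical t of 12.7. It would also average two versions of the programme.

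**The case against.** The strongest reply is that the plan already calls this a pilot. The closing paragraph of the SLUMBER-RD aims describes pilot testing that is preliminary to a large-scale trial. Aim 1 is feasibility, and no alpha, success rule or efficacy claim is set for the supplement. This stands and limits the weight of the point. It does not remove it: Aims 2 and 3 are still worded as tests, and C6 has no SLUMBER-RD analysis that would replace a framework powered for six units.

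Four stronger readings are tempting and are not supported.
- A reader might infer that the supplement rests on a single unit. Both units give before/after data and the aims speak of units. One unit is exact only for the revised version.
- A reader might infer that no hypothesis test is possible. A within-resident test of change can be run; only its attribution to the programme fails.
- A reader might infer that a null result is likely from size alone. At the parent target of .60, power without drift is Φ(.60/SE − 1.96), or 67% at N = 12 and 77% at N = 15 (59% and 70% with a paired t-test).
- A reader might infer that the investigators intend to claim efficacy. No text says so.

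It is also fair to object that the drift SD has no source. At .05 the error is hardly inflated, so the table shows a mechanism and does not measure this study's error rate. Parent attrition may not carry over either, since the supplement's follow-up is shorter.

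**Conclusion.** The point holds in this form: the design can estimate a before/after change on each unit, but cannot attribute it to SLUMBER-RD, so Aims 2 and 3 promise more than the data can give. That conclusion rests on the layout alone: one unit per version, no concurrent control, and one baseline for the outcomes of Aims 2 and 3. It does not depend on any assumed number. The false-positive rates, from about 5.5% to 24%, are illustrative. They depend on the assumed 12 to 15 residents, correlation of .5 and drift SD of .05 to .3. Because the work is a declared pilot, this is a matter of what is claimed and reported, and no data collection has to change.

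**What to change.** In A. Specific Aims (SLUMBER-RD), restate Aims 2 and 3 as pilot estimates of before/after change. Add a short SLUMBER-RD paragraph to C6 saying that:
- results are reported separately for unit 1 (development version) and unit 2 (revised version), without pooling;
- confidence intervals are labelled as reflecting within-unit variation only;
- no efficacy p-value or causal claim is made;
- resident-level variance, within-resident correlation, actigraph wear compliance and attrition are carried into planning of the large-scale trial;
- two units cannot usefully estimate between-unit variance, so that input must come from elsewhere.

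The cost is a more modest stated claim. Since these are the specific aims of a funding request, the rewording may need the funder's agreement. Visits, measures and schedule stay as they are.

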SLUMBER, every unit provides baseline and follow-up data. We will collect baseline data just prior to the intervention on a given unit and within 1 month after a 3-month exposure to the SLUMBER program. Facilities will encourage staff to continue to use intervention approaches after the 3-month intervention period. We will collect additional follow-up sleep and activity data with resident surveys and repeat wrist actigraph measures 3 and 6 months after the post-intervention period for all units to test for increased or continued benefit (sustainment) over time and assess for the possibility of reduced benefits over time (relapse). **From the intervention beginning and throughout the remaining study duration, real-time environmental data (noise via decibel meters) and observed sleep disturbance (by staff anonymous recording of sleep disturbances) will be available to SNF staff on a visible computer interface (described below) to facilitate continued use of SLUMBER strategies.** MDS 3.0 data collection will provide repeated measures of mood, cognitive function, and physical function for the full study duration (Figure 3). We selected a 3-month follow-up time point to strike a balance between sufficient time for intervention effects to emerge while considering the rapidly changing health status of LTC residents. Also, MDS data are collected quarterly and the intervention itself includes an initial mentoring session, three additional meetings over the next two months, and a follow-up session at the end of three months.

Supplement Design:

1. Overview: For this supplement application, we propose a 12-month intervention trial focused on dementia care SNF units using a modified comprehensive sleep improvement program, SLUMBER-RD, which is a mentored approach for unit staff. The study will be conducted in two urban SNFs with the goal of enhancing sleep quality, mood, cognitive performance, and activity engagement.

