Exclusion criteria include: 1) obtunded or comatose state, 2) inability to communicate verbally, 3) inability to consent and without surrogate, and 4) non-English and non-Spanish speaking. In keeping with QI strategies, all residents will be exposed to the environmental aspects of the intervention, as these strategies represent clinically proven non-experimental behavioral strategies with no perceptible harm. Recorded (anonymous) nurse observations, actions taken and observed outcomes will include all unit residents and will be recorded using the technology system to support staff-level interventions for any resident with a sleep behavioral issue. All staff input into this system is done without resident identification.

Step C. The collection of unit-level environmental data will focus on noise levels and documentation of resident symptoms in the MDS 3.0 (described below). MDS data will be de-identified and linked through unique random numbers. Data will include the routinely collected measures (MDS 3.0) by the facility on all consented residents as well as data from scheduled evaluations by research staff of residents who have consented to participate in evaluation components that are not part of usual clinical care. We have successfully employed this type of nested design for data collection in prior research. Federally mandated MDS 3.0 data is collected by the facility for all residents at admission and quarterly thereafter. We will obtain these data covering the time period of last collection beginning just prior to the introduction of the SLUMBER intervention, and ending at the conclusion of all data collection at each study site (nursing facility unit).

Steps D, E and F will comprise the SLUMBER intervention program itself. This process will begin as soon as the sleep team is identified, and will continue in sequence. Besides a “menu” of sleep improvement procedures, we will present the **3-component SLUMBER intervention** to unit staff: **1) Improving the nighttime sleep environment; 2) Increasing patient activity levels during the day and reducing daytime behaviors that lead to sleep disturbances at night; and 3) Identifying and assisting individual residents experiencing difficulties with sleep.** We will deliver the intervention over 3 months including the provision of five mentoring sessions and data feedback, which will cover the 3-month intervention period.

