C3. Data Collection Overview: Data collection includes the use of resident worn devices (actigraphs) that will download 3 days of data onto a computer interface collected at baseline, post-intervention, 3-months, and 6-months follow-up. Resident survey data and RA 3-day observations will be collected during the same time intervals. Decibel meters will link to a software platform via Bluetooth™ for continuous monitoring. Specific MDS 3.0 survey items that are collected quarterly by SNF staff will include the measures most proximal to and preceding baseline assessments. The RA will enter de-identified data from each in-person survey into a HIPAA-compliant REDCap electronic database hosted at NYU.⁸⁶ REDCap data will be electronically linked to MDS data. Throughout the study period MDS data will be collected from each SNF's data storage. DataCore, formed in collaboration with the NYU Langone Medical Center (NYULMC) Clinical and Translational Science Institute (CTSI), the Biomedical Informatics and Translational Library Programs, and the Department of Population Health, will provide enterprise level support to ensure data integrity during its capture, storage, management, extraction, and sharing. DataCore will merge these multiple data streams using unique study participant identifiers and will provide regular backups onto a secure server. [name] (study statistician) will access the data using remote desktop connection into NYULMC's secure Virtual Desktop Infrastructure (VDI). The VDI will be configured so that all analyses and derivative datasets performed by [name] will remain within the NYULMC datacenter.

Sources of materials: All data that is planned for collection will be obtained from surveys or interviews, wrist actigraphy, unit observations that are de-identified and administrative data all of which are maintained in electronic secure databases. Consenting subjects will participate in up to four actigraphy measurement periods, four observations, and four surveys collected during a 9-month period, depending on when they enter the study (determined by randomization procedures) and whether they leave the facility prior to the completion of the study period.

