For the analysis of routinely collected measures, the primary outcome concerns the test of the average of measures prior to the implementation of the intervention compared with the average of the measures after the implementation of the intervention. Using six steps in the stepped wedge design, the detectable standardized effect associated with the introduction of the intervention (the primary hypothesis) was computed as a function of the *final* sample size within each unit (columns) and the intra-cluster correlation (rows) shown in Table 7⁷⁷. All conditions specified have the ability to detect a medium or smaller effect ($< .50$). The smallest *final* sample size of N=10 provides sufficient power to detect an effect of 0.60 or smaller. Referring to Table 5, we see that all combinations of consent rate and attrition rate yield a *final* sample size of 10 or larger. Based on the results of Tables 7 and 5, the analyses for the routinely collected measures will have sufficient power to detect a clinically meaningful effect (i.e., a standardized effect of .60 or smaller).

Threats to Internal Validity: If outcomes improve with SLUMBER, we will consider explanations alternative to the treatment effect. While unlikely, residents may improve over time unrelated to the SLUMBER intervention. Use of routinely collected measures (MDS) will be investigated to identify possible improvements prior to the introduction of the intervention. MDS measures will also counterbalance the influence that the act of measuring has on the outcome since these measures are collected within routine care. Individuals with poorer outcomes might withdraw due to refusal, discharge or death, thereby creating an illusion of improvement. We will test for systematic attrition by comparing baseline scores of those who withdraw to those who remain. The stepped wedge design staggers introduction of the intervention to mitigate this threat. Spillover training and effects from one unit to the next unit in the same facility not yet engaged are also possible. We will include “manipulation checks” measuring intended changes between units (e.g., noise reductions) to assess whether contamination of sleep strategies occurred in the second unit at a facility before introducing SLUMBER to that unit.

C7. Data Storage and Confidentiality

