throughout the study period and additional face-to-face meetings linked to New York trips by Drs. [name] and [name] to conduct SLUMBER trainings. We already use conference call systems, Adobe Connect, and video conferencing quite ably to facilitate communication across institutions. Given that data will be captured electronically in real time, we will be able to manage intervention procedures and data quality and to review our progress at weekly meetings. All key research team members will participate in all aspects of the study design, data analyses, manuscript preparation and manual creation for a multi-site dissemination.

D. Risk/Benefit Assessment

Tasks	Year 1				Year 2				Year 3				Year 4			
	Q1	Q2	Q3	Q4												
Hiring																
Facility Leader Meetings	F1				F2				F3							All
Unit mentor meetings	U1	U1	U2	U2	U3	U3	U4	U4	U5	U5	U6	U6				
Equipment purchase, test																
Equipment set up on unit	U1	U2	U3	U4	U5	U6										
Baseline data gathering	U1	U2	U3	U4	U5	U6										
Unit SLUMBER training	U1	U2	U3	U4	U5	U6										
SLUMBER Intervention		U1	U2	U3	U4		U5	U6								
Follow-up data gathering		U1	U2	U3	U4	U5	U6									
Repeat Unit Follow-ups																
Web/MDS Data collection	F1		F2		F3											
Create single dataset																
Analysis																
Develop Program Manual																
Manuscripts																

(Q1=Quarter 1, etc.; F1=Facility 1, etc.; All=Combined Meeting of all facilities; U1=Unit 1, etc.)

D1. Risk

No pharmacological intervention or medical procedures will be used in this study. Rather this study aims to provide mentoring to nursing facility staff to provide sleep improvement procedures, which are consistent with high quality clinical care.

No interview data will be gathered without resident or proxy consent and although the study procedures are minimal risk, some questions may cause anxiety, embarrassment or be emotionally upsetting. The RA and Study coordinator will receive training in minimizing emotional impact or discomfort and will remind residents that they may discontinue participation or skip portions of the assessments that make them uncomfortable at any time. In the event of significant emotional upset, the PI will be notified and will intervene to address any concerns. A wrist actigraph could become uncomfortable to wear and with that complaint or concern, the device will be promptly removed. We have used the shortest possible recording period to minimize this risk.

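### The parent trial's MDS extraction window is stated inconsistently, and under Step C the promised check for improvement before the intervention has no within-unit trend to estimate

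*Combined protocol and SAP*

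**What the plan says.** Section C1, Step C, is the only place that gives both a start and an end for the parent trial's MDS extract. The start is: "We will obtain these data covering the time period of last collection beginning just prior to the introduction of the SLUMBER intervention". The end is: "ending at the conclusion of all data collection at each study site (nursing facility unit", so the window is set unit by unit. MDS assessments are made at admission and then quarterly.

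Other sections describe the window differently:

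- Section A5 (Study Design): "MDS 3.0 data collection will provide repeated measures of mood, cognitive function, and physical function for the full study duration".
- Section C3 points both ways. It takes the MDS items nearest to, and before, the baseline assessment, which agrees with Step C. It then says: "Throughout the study period MDS data will be collected from each" facility's data store.
- Section C8, Table 8, has a row "Web/MDS Data collection" labelled by facility (F1 to F3), not by unit.

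Two parts of section C6 depend on the window. Threats to Internal Validity says: "Use of routinely collected measures (MDS) will be investigated to identify possible improvements prior to the introduction of the intervention". The Power Analysis for Routinely Collected Measures says: "Using six steps in the stepped wedge design, the detectable standardized effect associated with the introduction of the intervention" was computed for Table 7, and concludes: "All conditions specified have the ability to detect a medium or smaller effect", meaning below .50.

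For the two-unit supplement, section A5 (Supplement Design) takes two quarters of MDS data before each resident's enrollment and gives interest in trend as the reason.

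**The concern.** An analyst could not write the extraction request from these sections. Step C gives one pre-intervention quarter per unit, with one record per consented resident. Full-study collection gives later units several. A facility-level window would give extra pre-intervention quarters only to the second unit in each facility.

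The choice decides whether a stated safeguard can work. Section C6 acknowledges that residents might improve for reasons unrelated to SLUMBER and names the MDS data as the means of looking for this. One pre-intervention quarter cannot show a trend within a unit or a resident. The six baselines do fall at different calendar times, but comparing them confounds time with unit.

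The safeguard carries weight because the section C6 model for these outcomes (PHQ-9, pain, BIMS, ADL) contains only Intv and IntvQtr. Without a calendar-time term, secular drift is attributed to the intervention terms. The window also decides whether Table 7 describes the data that will be analysed.

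**Working it through.** **1. Pre-intervention trend.** For p equally spaced quarterly values per resident, the information on a linear slope is Sxx = p(p² − 1)/12.

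- Step C: p = 1, so Sxx = 0. No slope can be estimated at any sample size.
- p = 2: Sxx = 0.5. p = 3: Sxx = 2.0.

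As an illustration, take six units, n=10 per unit, residual SD 1, independent residuals and the same residents followed. The slope detectable at 80% power (two-sided .05) is 2.802/√(6 × 10 × Sxx). That is .51 SD per quarter for p = 2 and .26 for p = 3.

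**2. Drift in the section C6 model.** Take one pre quarter (t = 0) and three post quarters (t = 1, 2, 3), in line with the nine-month follow-up in section C3. Let the outcome be s × t with no intervention effect.

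- Intv alone: post mean (1 + 2 + 3)s/3 = 2.0s, pre mean 0, so the apparent effect is 2.0s.
- Intv and IntvQtr: the post values lie on a line of slope s, so the IntvQtr coefficient is 1.0s. The Intv jump is that line read at IntvQtr = 0, minus the pre value.
  - If IntvQtr runs 0, 1, 2, the jump is 1.0s.
  - If it runs 1, 2, 3, the jump is 0.

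Section C6 defines IntvQtr as a count of quarters since the intervention and does not say which coding applies.

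**3. Table 7.** Inputs from section C6: six units, six steps, 80% power, two-sided .05, n per unit of 10, 15 and 20, ICC of 0, .20 and .40. The calculation is generalised least squares on unit-period means with fixed period effects and a random unit intercept. Within-unit SD is 1 and between-unit variance is τ² = ICC/(1 − ICC). Each unit's covariance is V = τ²J + I/n, and the detectable effect is (1.960 + 0.842) × SE.

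A complete layout of 6 units by 7 periods has 1 + 2 + 3 + 4 + 5 + 6 = 21 control unit-periods and reproduces all nine cells:

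| ICC | n=10 | n=15 | n=20 | Table 7 |
|---|---|---|---|---|
| 0 | .367 | .300 | .259 | .37/.30/.26 |
| .20 | .476 | .391 | .340 | .48/.39/.34 |
| .40 | .481 | .394 | .342 | .48/.39/.34 |

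Setting total SD to 1, dropping period effects, or using three sequences of two units did not reproduce it.

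**4. Same method and layout, Step C data.** Keeping only the last pre-intervention period in each unit leaves 6 control unit-periods:

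| ICC | n=10 | n=15 | n=20 |
|---|---|---|---|
| 0 | .470 | .384 | .332 |
| .20 | .550 | .453 | .394 |
| .40 | .558 | .458 | .397 |

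These are 16% to 28% larger than Table 7. Two of nine cells exceed .50. Power for an effect of .60 is at least 85% in every cell.

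**5. Step C data with a resident effect.** The section C6 model includes a resident intercept, which Table 7's method omits. With within-unit resident correlation ρ, V = τ²J + [ρJ + (1 − ρ)I]/n. The documents give no ρ; .3 to .5 is assumed. At n=10 and ICC 0/.20/.40:

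- ρ = .3: .43/.46/.47
- ρ = .5: .38/.39/.40

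No cell then exceeds .50.

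**The case against.** The strongest reply is that Step C may not be the intended window. Two other sections describe study-long collection, section A5 points to Figure 3, and Table 8's MDS row is by facility. Neither that figure nor the table's column alignment survives in the text available. This stands. It means that one cannot say that the trial will hold only one pre-intervention quarter, only that the sections disagree and that one of the readings disables the check.

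A second reply is that section C6 never promises a within-unit slope test, and that baselines taken at six calendar times allow some comparison. That comparison remains possible, but it cannot separate time from unit.

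Third, the missing calendar term is an analysis-model matter that the window does not cause. This also stands. Period terms could be fitted to Step C's data, and the pre/post contrast remains estimable. Lengthening the look-back without a calendar term would put more drift into the Intv jump, so the two changes belong together.

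Fourth, a reader might infer from step 4 that the MDS analyses are underpowered, or that the .60 benchmark is missed. The documents do not support that. The figures above .50 come from Table 7's unit-intercept method, occur only at n=10 (in Table 5, only at 45% consent with 40% attrition), and disappear under the assumed resident correlations. A reader might likewise infer that drift always inflates the Intv jump; that depends on a coding that the plan leaves open.

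**Conclusion.** The inconsistency is real and should be resolved before the data are requested. If Step C governs, the check for improvement before SLUMBER has no within-unit or within-resident trend to estimate, whatever the sample size. The supplement's two-quarter look-back shows that the investigators recognise what a trend requires.

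With one pre and three post quarters and no calendar term, a linear drift of s per quarter enters the IntvQtr slope in full, or gives 2.0s if Intv is fitted alone. Its share of the Intv jump is 1.0s or 0, depending on coding.

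The power point is secondary. Table 7 describes 21 control unit-periods and Step C supplies 6, so the table needs restating if Step C is meant. A breach of .50 is not certain, and no miss of .60 is claimed. These conclusions assume quarterly records, linear drift and Table 7's layout of seven periods; the resident correlation is an assumption.

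**What to change.** State one window and align sections A5, C1 (Step C), C3 and Table 8 with it. The preferred window takes consented residents' quarterly MDS records on all six units from at least two quarters before the first unit's introduction (or from admission, if later) to a stated common end, provided that consent and IRB approval cover the earlier records.

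Alongside it:

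- add a calendar-quarter term to the section C6 model and state how IntvQtr is coded;
- pre-specify the pre-trend test;
- report residents per unit-quarter;
- recompute Table 7 and its conclusion for the chosen window and model.

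If the narrow window is meant, restate Table 7 for it and delete the pre-trend claim from Threats to Internal Validity.

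The cost is a longer electronic extract of records that the facilities already hold, consent wording and one more model term. One weakness remains: consent is taken at each unit's baseline, so early quarters contain only residents who stayed until then. An apparent pre-trend may reflect that selection, and the report should say so.
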